**COLUMBIA UNIVERSITY
MEDICAL CENTER**

TITLE: A Phase Ib/II, Open-label, Multicenter Study of the Selective HDAC6 Inhibitor, ACY-1215, for the Treatment of Patients with Relapsed or Refractory Lymphoid Malignancies

Coordinating Center: Columbia University Medical Center (CUMC)
Participating Centers: H. Lee Moffitt Cancer Center & Research Institute

**Principal Investigator/
Study Chair:** [name]
Assistant Professor of Medicine and Experimental Therapeutics
Center for Lymphoid Malignancies
Herbert Irving Comprehensive Cancer Center
Columbia University Medical Center
[contact]

Co-Investigators: [name], PhD
Professor of Medicine and Experimental Therapeutics
Director, Center for Lymphoid Malignancies
[contact]

[name], Ph.D.
Assistant Professor of Clinical Medicine
[contact]

[name]
Instructor in Clinical Medicine
[contact]

[name]
Site Principal Investigator
H. Lee Moffitt Cancer Center & Research Institute
[contact]

CUMC Protocol #: *AAAM4054*

Protocol Type / Version # / Version Date: Amendment 3 Ph II / Version 6 / 23 November 2016

PROTOCOL SYNOPSIS

Title:

A Phase Ib/II, Open-label, Multicenter Study of the Selective HDAC6 Inhibitor, ACY-1215, for the Treatment of Patients with Relapsed or Refractory Lymphoid Malignancies

Study Design:

This will be an open-label, single agent, multi-institutional phase Ib/II study of ACY-1215 for the treatment of patients with relapsed or refractory lymphoid malignancies. The target population will include patients with histologically confirmed relapsed or refractory non-Hodgkin's lymphoma or Hodgkin's lymphoma, with an expansion cohort of patients with mantle cell lymphoma.

Phase Ib Objectives:

- Establish the safety of 2 dose schedules of ACY-1215 in patients with relapsed or refractory lymphoid malignancies treated with ACY1215.

Phase II Objectives:

Primary Objectives

- Determine the overall response rates (CR plus PR) in patients with relapsed or refractory lymphoid malignancies treated with ACY1215.
- Determine the progression free survival (PFS) and Time to Treatment Failure (TTF) in patients with relapsed or refractory lymphoid malignancies treated with ACY1215.
- Determine the duration of response (DOR) in patients with relapsed or refractory lymphoid malignancies treated with ACY1215.

Secondary Objectives

- Determine the safety and tolerability of ACY-1215 in patients with relapsed or refractory lymphoid malignancies.
- Evaluate the pharmacokinetic (PK) profile of ACY-1215 as a single agent in patients with lymphoid malignancies.
- Evaluate and compare pharmacodynamic (PD) endpoints with PK endpoints. Proposed PD markers of target effect in paired pre- and post ACY-1215 tissue biopsies peripheral blood, and serum samples would include: HDAC6, acetylated- α -tubulin, total

polyubiquinated proteins, GRP-78, CHOP, XBP-1, IL6, IL10, STAT3, AKT, NFkB level of expression, and Treg levels

- Conduct Magnetic Resonance Spectroscopy Imaging (MRS) for the detection of early signal of response and predict overall response.

Target Population

Patients with relapsed or refractory non-Hodgkin's lymphoma and Hodgkin's lymphoma

Inclusion Criteria

1. Patients must have histologically confirmed relapsed or refractory Non-Hodgkin's Lymphoma or Hodgkin's Lymphoma (WHO criteria), for which they are unwilling or unable to undergo an autologous stem cell transplant. Patients may have relapsed after prior stem cell transplant.
2. Must have relapsed or refractory disease. No upper limit to number of prior therapies.
3. Patients must have measurable disease
4. Patients must be age ≥ 18 .
5. Patients must be ECOG performance status ≤ 2 . (See definition in Appendix).
6. Patients must have adequate organ and marrow function.
7. Patients must utilize adequate contraception.
8. Patients must have the ability to understand and sign informed consent.

Exclusion Criteria

1. Prior Therapy
 - a. Patients who have had chemotherapy or radiotherapy within 2 weeks of study drug treatment or those who have not recovered from adverse events due to agents administered
 - b. No monoclonal antibody within 3 months unless evidence of disease progression.
2. Patients may not be receiving any other investigational agents.
3. Patients with known central nervous system metastases, including lymphomatous meningitis
4. Any known cardiac abnormalities such as:
 - Congenital long QT syndrome
 - QTc interval ≥ 500 milliseconds;
5. Uncontrolled inter-current illness
6. Pregnant or nursing women
7. Patient is known to be Human Immunodeficiency Virus (HIV)-positive

8. Patients with active Hepatitis A, Hepatitis B, or Hepatitis C infection
9. Patient has a history of surgery that would interfere with the administration or absorption of the oral study drugs

Treatment Plan

Phase Ib:

Patients will be accrued sequentially to two dose cohorts (Arm A and Arm B) of ACY1215. Upon completion of enrollment of 3 patients to Arm A and a safety assessment has occurred, patients will be allowed to be enrolled to Arm B. All patients will take the assigned dose of ACY1215 for 28 consecutive days. Patients enrolled into Arm A will take ACY1215 160mg once daily, whereas patients enrolled into Arm B will take ACY1215 160mg twice daily. ACY-1215 will be supplied as a liquid for oral administration (PO). Each dose will be administered at least 1 hour after ingestion of food followed by at least 4 ounces of water. Patients will be instructed not to ingest food or other oral medication for at least 2 hours after each ACY-1215 dose.

Phase II:

All patients will take the assigned dose of ACY1215 for 28 consecutive days. The schedule of ACY1215 will be determined based on the safety data from the Phase Ib. Recommended Phase II dose will be based on a discussion with the sponsor and collaborating investigators, with a pre-planned intent to select the schedule that allows the highest dose intensity safely. ACY1215 will be supplied as a liquid for oral administration (PO). Each dose will be administered at least 1 hour after ingestion of food followed by at least 4 ounces of water. Patients will be instructed not to ingest food or other oral medication for at least 2 hours after each ACY-1215 dose.

Duration of Treatment

There is no limit to the number of cycles of therapy. Patients may continue on treatment until they develop progressive disease (PD) or experience an unacceptable toxicity that precludes further treatment.

After discontinuation of therapy, patients will be followed on an every 3 month (+/- 1 week) basis for 1 year or until development of progressive disease or initiation of alternative therapy in order to determine the duration of response.

Patients will be treated until one of the following events:

- Disease progression
- Unacceptable adverse event(s)
- Withdrawal of consent

- General or specific changes in the patient's condition that render the patient unacceptable for further treatment in the judgment of the investigator
- An event that in the judgment of the treating physician warrant's discontinuation of therapy.
- Termination of the study

Study Endpoints

Phase Ib:

The primary endpoint of the study is:

- Establish the safety and tolerability of ACY1215 in two dosing schedules.

Phase II:

The primary endpoint of the study is:

- The anti-tumor activity of ACY-1215, as measured by:
 - Objective response rate (complete response [CR] + partial response [PR]) assessed according to International Harmonization Project revised Criteria (2007)

Secondary endpoints of the study are to:

- Define the duration of response
- Define the rate of progression free survival
- Define safety and adverse events
- Define the exposure response analyses including biomarkers relating to intracellular protein acetylation.
- Describe the Single- and multiple-dose ACY-1215 pharmacokinetic profile.
- Describe changes in MRS signals with response to study drug

Sample Size

Phase Ib:

Three patients will be sequentially enrolled in one of two cohorts: Arm A and Arm B for a total of six patients (3 in each arm). If $\leq 33\%$ of patients ($N \leq 1$) experiences a dose limiting toxicity (DLT) in a cohort, the cohort will be expanded to 6 patients (3+3). If there are $\leq 33\%$ ($N \leq 2$ DLTs), the cohort will be further expanded to a total of 10 patients (3+3+4). The maximum total number of patients for both Arms A and B with full expansions will total of 20. If more than 1/3 or 2/6 patients experience a DLT, there will be no expansion.

Phase II:

Utilizing the Simon 2 Stage Minimax design, an estimated 40 patients will be needed to determine efficacy at a power of 0.80 and type I error of 0.05. For Stage I, 22 patients

will be enrolled of which 2 must achieve a response to allow for recruitment of patients into Stage 2. Stage 2 will enroll 18 patients of which 8 responses would be needed to attain an efficacy of 25%. An expansion cohort of 20 patients with relapsed or refractory mantle cell lymphoma patients will be assessed to evaluate efficacy in this subtype. The total number of patients accrued to the Phase II component of the study will equal 60.

Safety

Patients will be monitored carefully for the development of adverse events as well as clinical and/or radiographic evidence of disease response. Adverse events will be evaluated according to criteria outlined in the NCI Common Terminology Criteria for Adverse Events (CTCAE), version 4.0.

Figure 1: Schema

[figure not shown]

TABLE OF CONTENTS

	Page
1. OBJECTIVES	1
1.1 Phase Ib	1
1.2 Phase II	1
2. BACKGROUND	1
2.1 Background on lymphoid Malignancies	1
2.2 ACY-1215	2
2.3 Rationale for Phase Ib Study Design	11
3. PATIENT SELECTION	12
3.1 Inclusion Criteria for Lymphoma	12
3.2 Exclusion Criteria	13
3.3 Inclusion of Women and Minorities	13

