2.2.4 ACY-1215 Chemical Structure

Figure 3: Chemical Structure

The molecular formula of ACY-1215 is $C_{24}H_{27}N_5O_3$, its molecular weight is 433.5, and its chemical name is: 2-(Diphenylamino)-N-(7-(hydroxyamino)-7-oxoheptyl)-pyrimidine-5-carboxamide.

2.2.5 Product description:

ACY-1215 is a histone deacetylase (HDAC) inhibitor that has not been assigned either an International Nonproprietary Name (INN) or a United States Adopted name (USAN). The active pharmaceutical ingredient is a white to off white crystalline solid with a melting point of

approximately 192°C. ACY-1215 is highly soluble in dimethyl sulfoxide, soluble in methanol, and poorly soluble in acetone, chloroform, and water at less than 1 mg/mL. The label attached to each vial contains the appropriate information, including product name and amount, lot number, directions for storage, date of manufacture, name of Sponsor, and the following statement:

“Caution: New Drug--Limited by Federal (or United States) law to investigational use.”

Study drug labels will not contain any statement that is false or misleading in any manner or represent that the study drug is safe or effective for the purposes for which it is being investigated.

2.2.6 Solution preparation:

ACY-1215 will be supplied by Acetylon Pharmaceuticals as a liquid for oral administration in 20mL clear type I glass vials. Each vial will contain 15 mL of a 12 mg/mL solution for a total of 180 mg per bottle.

2.2.7 Storage requirements:

ACY-1215 will be stored at -20°C. Additional storage conditions and dose preparation instructions will be provided in detail within the Pharmacy Manual. All study drug must be stored in a safe and locked place with no access by unauthorized personnel.

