This is a phase II, single-arm, multicenter, open-label study in patients with relapsed or relapsed/refractory lymphoma. Utilizing the Simon 2 Stage Minimax design, an estimated 40 patients will be needed to determine efficacy at a power of 0.80 and type I error of 0.05. Using this design, there will be an early stopping rule if $< 10\%$ achieve a response in Stage 1. Twenty-two ($N=22$) patients will be accrued to Stage 1, of which 2 patients are required to achieve a response to allow accrual to Stage 2. Patients accrued to Stage 1 of the Phase II will be of all lymphoid malignancy subtypes including those with mantle cell lymphoma (MCL). Eighteen patients ($N=18$) will be treated in Stage 2, of which 8 responses would be needed to attain an efficacy of at about 25%. The safety, tolerability, single- and multiple-dose PK, pharmacodynamics, and anti-tumor activity of ACY-1215 also will be evaluated. Simultaneously in Stage 2, an additional cohort of 20 mantle cell lymphoma patients will be assessed to evaluate for a signal of efficacy in this subtype. These patients will be enrolled in parallel to the phase II study. Assuming success in Stage I, enrollment to Stage 2, and expansion of MCL cohort, the total number of patients will be 60 (Stage 1 $N=22$, Stage 2 $N=18$, MCL focused Expansion Phase $N=20$).

5.1.3 Treatment plan common to both Phase Ib and Phase II:

After executing written informed consent, patients will be evaluated for study eligibility during the Screening period within the Screening period before Cycle 1, Day 1 [C1D1]. Patients determined to be eligible will be treated on study. Patients will be evaluated on Days 1, 8, and 15 of Cycle 1.

On study drug administration days that coincide with scheduled study center visits, ACY-1215 will be administered at the study center.

- One cycle of therapy is comprised of 28 or 56 doses of ACY-1215.
- Administration of the study drugs will be allowed within 48 hours of the scheduled dates.
- Missed doses will not be made up.

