5.1.2.1 Rationale for the Dose Selected

In this study, ACY-1215 will be examined as a single agent administered by the oral route 28 consecutive days of a 28 day cycle in patients with relapsed and/or relapsed-refractory lymphoma to assess clinical response, safety, tolerability, PK and PD of ACY-1215.

The rationale of the dosing schedule of ACY 1215 is based on results from a Phase I monotherapy trial in which no maximally tolerated dose (MTD) was established when ACY-1215 was dosed once daily on days 1-5 and days 8-13 of a 21 day cycle up to a dose of 360 mg. Pharmacokinetics were similar at doses of 160 mg (C_{max} 626 +/- 150 ng/mL and $AUC_{0-\infty}$ 1300 +/- 533 ng*h/mL) to higher doses. The half-life of elimination ranged from 3-4 hours and no

accumulation of drug was observed. Dosing at 160 mg and above demonstrated acetylation of tubulin, the pharmacodynamic marker of HDAC6 inhibition, in peripheral mononuclear cells for all patients in these cohorts. Doses above 160 mg lead to off target effects demonstrated by acetylation of histone 3 and increased toxicities. Given the relatively short half-life (~3 h) and safety profile of ACY-1215, twice daily dosing will also be explored to maximize the dose intensity while limiting the toxicity. Twice daily administration of ACY-1215 at 160 mg is expected to approximately double the daily exposure (AUC) to ~4000 ng·h/mL with a minimal impact on maximal plasma levels and no anticipated accumulation, since >95% of the administered dose will have been cleared before the next dose administration. 28-day repeat dose GLP toxicology studies in dogs showed that exposure levels of 15,000-26,800 ng·h/mL were attained with minimal to mild changes in blood cell parameters and minimal changes in body weight that were partially to fully recoverable. Twice daily dosing is therefore not anticipated to change the safety profile of ACY-1215. Accordingly, once daily and BID dosing at 160 mg will be explored in the Phase 1b section of the trial.

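### Table 1 equates the 160 mg dose with one vial, but section 2.2.6 puts 180 mg in a vial; the protocol gives no volume per dose to settle which amount is taken

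*Combined protocol and SAP*

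**What the plan says.** The dose is 160 mg throughout. The synopsis (Treatment Plan, Phase Ib) says "Patients enrolled into Arm A will take ACY1215 160mg once daily, whereas patients enrolled into Arm B will take ACY1215 160mg twice daily", and sections 5.1.1, 5.1.2 (Regimen Description) and 5.1.2.1 use the same figure. None of these mentions vials.

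Two places describe the vial, and they differ:

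- Table 1 (Regimen Description, at the end of section 5.1.3) gives the dose as 160 mg and adds in parentheses that this is one vial.
- Section 2.2.6 (Solution preparation) says: "Each vial will contain 15 mL of a 12 mg/mL solution for a total of 180 mg per bottle".

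On preparing a dose, section 2.2.7 says only: "Additional storage conditions and dose preparation instructions will be provided in detail within the Pharmacy Manual". Section 5.1.3 fixes the number of doses: "One cycle of therapy is comprised of 28 or 56 doses of ACY-1215". Section 5.1.2.1 gives the reason for not going above 160 mg: "Doses above 160 mg lead to off target effects demonstrated by acetylation of histone 3 and increased toxicities".

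**The concern.** The regimen table is what a site is likely to work from, and it offers two measures of a dose, milligrams and vials. By section 2.2.6 they are not the same amount. A pharmacist or patient who follows the milligrams and one who follows the vial would deliver different doses, and the protocol text does not say which reading is meant.

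Three features of the trial make this more than a typing matter. First, treatment is outpatient. Doses are given at the center only on visit days: a few days in Cycle 1 and, by the study calendar, Day 1 of each later cycle. The remaining doses are taken at home. Second, the dose rationale treats 160 mg as a level above which off-target effects and toxicity rise, and a whole vial as described in section 2.2.6 lies above it. Third, section 12.5 promises percent of expected dose, actual dose and dose intensity by cycle, and all of these need the milligrams actually taken. The patient log in section 5.3 collects times of food and drug, not volume.

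**Working it through.** **Inputs**

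- Dose: 160 mg (synopsis; Table 1).
- Fill volume 15 mL and concentration 12 mg/mL (section 2.2.6).
- Doses per cycle: 28 or 56 (section 5.1.3).

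**Step 1: reproduce the stated vial content.** Volume × concentration = 15 × 12 = 180 mg. This equals the total in section 2.2.6, so the three figures there agree with one another.

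**Step 2: compare a whole vial with the dose.** 180 − 160 = 20 mg; 180 / 160 = 1.125, an excess of 12.5%.

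**Step 3: what 160 mg is in volume.** 160 / 12 = 13.33 mL, leaving 15 − 13.33 = 1.67 mL in the vial. This is arithmetic on the stated concentration, not a proposed instruction.

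**Step 4: could one slip in section 2.2.6 explain it?** For a vial to hold exactly 160 mg, the stated total would have to change together with either the volume (to 13.33 mL) or the concentration (to 160 / 15 = 10.67 mg/mL). At least two of the three figures would be wrong. This does not settle which entry is in error.

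**Step 5: size by schedule, if whole vials were taken.**

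| Schedule | mg/day at 160 mg | mg/day at 180 mg | mg/cycle at 160 mg | mg/cycle at 180 mg | Excess per cycle |
|---|---|---|---|---|---|
| Once daily (28 doses) | 160 | 180 | 4,480 | 5,040 | 560 |
| Twice daily (56 doses) | 320 | 360 | 8,960 | 10,080 | 1,120 |

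**Step 6: reduced doses.** Table 2 provides for reduction to 75% of dose. Taken on 160 mg that is 0.75 × 160 = 120 mg; taken as three-quarters of a 180 mg vial it is 0.75 × 180 = 135 mg. The ambiguity carries over, again with no volume stated.

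**Step 7: look for text that resolves it.** No section gives a volume in mL for a dose, describes part of the fill as overfill, or says what to do with a remainder.

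**The case against.** The strongest reply is that the two entries can be read together. One vial may mean one vial opened per dose, with 160 mg measured out of a 180 mg fill. A Pharmacy Manual that prescribed such a withdrawal would fit both Table 1 and section 2.2.6. The milligram dose is stated consistently, and Table 2 already presupposes amounts other than a whole vial. This stands. A reader might infer that patients are being over-dosed, or that the safety and response data describe 180 mg under a 160 mg label. The documents support neither, because nothing tells anyone to take the whole vial.

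The second reply concerns consequence. Section 2.2.15 reports an exposure plateau from 160 mg upward, and sections 2.3 and 7.3.4 report no dose-limiting toxicity up to 360 mg. This also stands in part: the documents do not show that 20 mg more per dose would change toxicity counts, the choice of schedule or response. It does not settle the matter. That experience comes from 15 myeloma patients (section 7.3.1), only two of them at 360 mg, dosed once daily on an intermittent schedule. No level between 160 and 240 mg was tested. Section 5.1.2.1 still attributes increased toxicity to doses above 160 mg.

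The third reply is that the safeguards exist already: section 12.5 plans actual dose received, and section 2.2.10 requires drug accountability. They help only if volume is captured. If one vial is used per dose, vial counts are the same whether 160 mg or 180 mg is taken. The accountability items listed do not include residual volume.

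**Conclusion.** The inconsistency is real and lies between Table 1 and section 2.2.6; the synopsis sentence that sets 160 mg contains no error. If Table 1 is taken to mean a whole vial, each dose is 20 mg (12.5%) above the stated dose: 180 rather than 160 mg/day once daily, or 360 rather than 320 mg/day twice daily. Those figures assume that section 2.2.6 is correct and that the full 15 mL is taken.

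Whether anyone would be dosed that way depends on a manual that is not among the documents, so the finding is an unresolved conflict in the regimen table, not a demonstrated dosing error. No sample size, error rate or decision rule changes. What is affected is the definition of the delivered dose and the dose-intensity figures built on it. This should be corrected because the drug is a liquid taken mainly at home and the protocol itself attaches meaning to exceeding 160 mg.

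**What to change.** 1. Reconcile Table 1, section 2.2.6 and the Pharmacy Manual against pharmacy and supply records, and correct whichever entry those records show to be wrong. This review takes no position on which it is.
2. State the protocol dose in Table 1 in both mg and mL. If one vial is meant as one vial used per dose with a measured withdrawal, say so.
3. Record the volume taken for each dose, and compute the exposure and dose-intensity summaries of section 12.5 in mg from it.
4. If any patient was dosed by the whole vial, report the actual mg received.

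The cost is a one-line correction to Table 1 or section 2.2.6, a notice to pharmacies and sites, and one case report form field with a matching entry in the patient log. No patients or procedures are added.

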12.1 Statistical Methods

12.1.1 Phase Ib:

The study will follow the similar principles of a standard 3+3 dose escalation study in which less than one third of patients enrolled to a particular Arm must not have a dose limiting toxicity to allow for expansion. Three patients will be sequentially enrolled in one of two cohorts: Arm A and then after a safety assessment has occurred, Arm B for a total of six patients (3 in each arm). If $\leq 33\%$ of patients ($N \leq 1$) experiences a dose limiting toxicity (DLT) in a cohort, the cohort will be expanded to 6 patients. If there are $\leq 33\%$ ($N \leq 2$ DLTs), the cohort will be further expanded to a total of 10 patients (3+3+4). The total number of patients for both Arms A and B with full expansions will total of 20. If more than 1/3 or 2/6 patients experience a DLT, there will be no expansion. Safety data obtained from this Phase Ib will be analyzed by the sponsor and collaborating investigators to recommend a Phase II dose.

12.1.2 Phase II:

The study will employ the minimax Simon 2-stage design. In Stage 1, 22 patients will be enrolled. If < 2 patients experience an objective tumor response (defined as CR, or PR, as outlined by the 2007 International Harmonization Project criteria), the study will be discontinued. If 2 or more of the first 22 patients experiences CR, or PR, additional 18 patients will be enrolled in Stage 2. Enrollment into Stage 2 will begin only after least 2 objective response have been observed in Stage 1. (Enrollment into Stage 2 need not be delayed until the response status of all 22 Stage 1 patients is known.) The design parameters are as follows:

- 0.15: unacceptable response rate.

- 0.25: target response rate.
- $\alpha = 0.05$: the probability of declaring the drug effective when the true response probability is less or equal to 0.15.
- $\beta = 0.20$: the probability of declaring the drug as not effective when its true response probability is as large or larger than the target response rate 0.30.

Once enrollment begins for stage 2 of the study, an additional 20 patients will be enrolled per lymphoma subtype, specifically Mantle Cell Lymphoma. Therefore the total number of patients estimated to be enrolled is 60.

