12.11 Procedures for Reporting Deviations to Original Statistical Analysis Plan

A formal statistical plan for the analysis and presentation of data from this study will be prepared before database lock. Deviations from the statistical analyses outlined in this protocol will be indicated in this plan; any further modifications will be noted in the final clinical study report.

13. Accrual Rate

We estimate accrual of an average of 6 patients per month across the study centers, with a goal of completing accrual within 12-18 months.

14. Administrative Requirements

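### The only final success rule (8 responses among the 18 Stage 2 patients, labelled 25%) does not fix a cut-off, and no reading of it gives alpha 0.05 with power 0.80 at the stated null rate of 0.15

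*Combined protocol and SAP*

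**What the plan says.** The synopsis (Sample Size, Phase II) names a Simon two-stage minimax design: "an estimated 40 patients will be needed to determine efficacy at a power of 0.80 and type I error of 0.05". Stage 1 has 22 patients, "of which 2 must achieve a response to allow for recruitment of patients into Stage 2". The final criterion follows: "Stage 2 will enroll 18 patients of which 8 responses would be needed to attain an efficacy of 25" per cent. Section 5.1.2 (Phase II) repeats it: "of which 8 responses would be needed to attain an efficacy of at about 25" per cent.

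Section 12.1.2 gives the design parameters. The null rate is "0.15: unacceptable response rate" and the target is "0.25: target response rate". Alpha is 0.05 and beta is 0.20, but the beta bullet defines beta "when its true response probability is as large or larger than the target response rate 0.30". The section repeats the Stage 1 gate (at least 2 of 22) and the 18 further patients. It states no number of responses for success at the end.

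Section 12.3.2.1 plans an estimated response rate with an exact 95% confidence interval. Section 12.9.2 sets the timing of the final analysis. Neither gives a threshold. Section 12.11 adds: "A formal statistical plan for the analysis and presentation of data from this study will be prepared before database lock".

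**The concern.** Taken literally, the sentence asks for 8 responses among the 18 Stage 2 patients, which is 44%, yet the same sentence calls this 25%. A Simon design normally counts both stages together, which suggests 8 of 40, but that is 20%. Only by adding the Stage 1 minimum of 2 does one reach 25%, as 10 of 40. The documents do not choose among these.

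This is the go/no-go threshold for the primary endpoint. A final count of 8 or 9 in 40 is a success under 8 of 40. It is a failure under 10 of 40, and also under the literal rule, which with the gate of 2 needs at least 2 + 8 = 10 in total. The only later document that could settle the matter is a statistical plan due before database lock. In an open-label single-arm trial, responses may be known by then.

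**Working it through.** **Inputs.** n1 = 22, n2 = 18, N = 40, continue at 2 or more responses, alpha 0.05, power 0.80 (synopsis; Sections 5.1.2 and 12.1.2). Null rate p0 = 0.15; target rate p1 = 0.25 in one bullet and 0.30 in another (Section 12.1.2). The 20 mantle cell expansion patients are not counted.

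**Percentages.** 8/18 = 44.4%; 8/40 = 20.0%; (2 + 8)/40 = 25.0%.

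**Formulas (exact binomial).**
- Cumulative cut-off c: sum over x ≥ 2 of P(Bin(22, p) = x) × P(Bin(18, p) ≥ c − x).
- Literal rule: P(Bin(22, p) ≥ 2) × P(Bin(18, p) ≥ 8). At p = 0.25 this is 0.985 × 0.0569 = 0.056.

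**Probability of declaring success, Stage 1 gate of at least 2 of 22:**

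| Rule | p = 0.10 | p = 0.15 | p = 0.20 | p = 0.25 | p = 0.30 |
|---|---|---|---|---|---|
| ≥8 of 18 (Stage 2 only) | 0.0001 | 0.002 | 0.016 | 0.056 | 0.140 |
| ≥8 of 40 | 0.042 | 0.243 | 0.561 | 0.816 | 0.944 |
| ≥10 of 40 | 0.005 | 0.067 | 0.268 | 0.560 | 0.804 |
| ≥11 of 40 | 0.0015 | 0.030 | 0.161 | 0.416 | 0.691 |

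The 0.15 column is the type I error at the stated null. The 0.25 and 0.30 columns are power at the two stated targets. At p0 = 0.15:
- 8 of 18 holds alpha but has almost no power.
- 8 of 40 has the power, but its alpha is about five times the nominal value (0.243/0.05 = 4.9).
- 10 of 40 misses alpha and reaches 0.80 power only at 30%.
- 9 of 40 also fails (alpha 0.135). 11 of 40 restores alpha but loses power.

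**Can any design with N = 40 meet the claim?** A full search over two-stage designs with N = 40 and p0 = 0.15 finds none with alpha ≤ 0.05 and power ≥ 0.80, at p1 = 0.25 or 0.30. The minimax designs at alpha 0.05 and power 0.80 are:

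| p0 vs p1 | Continue if | Success if | Alpha | Power |
|---|---|---|---|---|
| 0.15 vs 0.25 | ≥9 of 55 | ≥21 of 97 | 0.049 | 0.801 |
| 0.15 vs 0.30 | ≥4 of 23 | ≥12 of 48 | 0.045 | 0.804 |
| 0.10 vs 0.25 | ≥3 of 22 | ≥8 of 40 | 0.040 | 0.803 |

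Only the last returns the protocol's 22, 40 and 8. So 8 is probably that design's cumulative cut-off, and p0 = 0.15 does not belong to it. This is an inference: no section states 0.10, or 8 of 40.

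**Where the cumulative readings disagree.** P(8 or 9 of 40) is the ≥8 row minus the ≥10 row:
- p = 0.15: 0.2427 − 0.0672 = 0.18
- p = 0.20: 0.5607 − 0.2680 = 0.29
- p = 0.25: 0.8161 − 0.5602 = 0.26

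**The case against.** The best reply is that any statistician reads a Simon cut-off cumulatively, so 8 of 18 would not be applied. On this view 25% is the design's target rate rather than an observed proportion, and the rule is simply 8 of 40. That is the likeliest intention, and the 0.056 power figure then describes an improbable analysis. The 25% label can also be squared arithmetically, through 10 of 40. But neither route rescues the plan: 8 of 40 has alpha 0.243 at the protocol's own null rate, and 10 of 40 has 0.067.

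A second objection is that the failure on alpha and power comes from the rates in Section 12.1.2 rather than from the sentence. That is partly true, since 8 of 40 works at a null of 0.10. It is why the rates must be settled first. The cut-off would still be missing from Section 12.1.2.

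Third, Sections 5.1.2 and 12.9.1.2 also stop the trial if fewer than 10% respond. Since 2/22 = 9.1%, that implies a gate of at least 3 of 22. This is correct and needs reconciling, but it changes little: with a gate of 3, 8 of 40 has alpha 0.234 and power 0.803 at 25%.

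Fourth, the response rate will be reported with an exact interval whatever the cut-off, deviations must be declared, and a monitoring board oversees interim analyses. These provisions help transparency, but none supplies a cut-off.

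**Conclusion.** The concern holds and must be fixed. The protocol has one final success criterion. Its literal wording contradicts its own percentage, its denominator is open, and the statistical section does not restate it. At p0 = 0.15 the three readings give type I error from 0.002 to 0.243 and power at 25% from 0.056 to 0.816; none meets both stated targets. If the true response rate lies between 15% and 25%, the chance of a result on which the two cumulative readings disagree is about 18% to 29%.

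The figures assume exact binomial responses, all 40 patients evaluable and the gate of at least 2 of 22. The failure at p0 = 0.15 is certain; that the design was meant for 0.10 versus 0.25 is only likely.

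**What to change.** Make one amendment, in this order:

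1. In Section 12.1.2, confirm the null rate and choose one target rate (0.25 or 0.30).
2. Replace the sentence in the synopsis and Section 5.1.2, and add to Section 12.1.2, one cumulative cut-off over the 40 Stage 1 and Stage 2 patients, excluding the mantle cell expansion cohort. Remove the phrase about attaining 25% efficacy.
3. State the alpha and power which that cut-off delivers:
   - If 0.10 versus 0.25 is confirmed: active at 8 or more of 40 (observed rate at least 20%), not active at 7 or fewer. With a gate of at least 3 of 22, alpha is 0.040 and power 0.803; with at least 2 of 22, 0.042 and 0.816.
   - If 0.15 is kept: do not pair 8 of 40 with a stated alpha of 0.05. Restate the properties at N = 40. For example, 11 or more of 40 gives alpha 0.030 and power 0.42 at 25% or 0.69 at 30%.
4. Make the Stage 1 gate agree across Sections 5.1.2, 12.1.2 and 12.9.1.2.
5. State which patients make up the 40. Section 12.3.2.1 treats some as un-evaluable, and Sections 4.5 and 6.1 replace patients who miss more than 10% of planned dose.

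Fix the cut-off by amendment before responses are reviewed, not in the later statistical plan. If responses have already been seen, say so in the amendment. The cost is a statistician's decision and text changes in a few sections. Neither route at N = 40 adds patients; keeping 0.15 means accepting lower stated power.
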